6.1.2 Visit 2, Day 1 Randomization

- Perform physical exam, including weight
- Perform investigator skin assessment of the upper arm where patches are intended to be applied
- Record vital signs: temperature, respiratory rate (RR), blood pressure (BP), and heart rate (HR)
- Record concomitant medications, including medication taken to treat cluster headaches
- Urine pregnancy for all WOCBP
- Record Adverse events
- Train the subject on how to apply the patches to the upper arm with the demo applicator and have the subject practice applying the demo patches to his/her arm 2-3 times (more is allowable, if necessary)
- Review the definition of a qualifying cluster headache for the study with the subjects
- Record that the subject can apply patches with the applicator unaided
- Reconfirm subject's eligibility based on inclusion/exclusion criteria
- Randomize subject
- Dispense CTM kit that includes the applicator and one dose (each dose consists of 2 patches) as assigned by the RTSM in Medidata

- Provide instructions for scheduling the next visit within 1-8 days of experiencing and treating a qualifying cluster headache with C213
- Remind the subject that if rescue therapy is required, rescue therapy other than a triptan or ergot is permitted at or after 20 minutes post study drug administration.
- Provide eDiary training necessary and dispense the eDiary

6.1.3 Double-Blind Treatment Phase: Day 1 through up to 48 Weeks [336 Days + or – 7 days]

Subjects will have up to 48 weeks to confirm and treat a qualifying cluster headache. Subjects will be instructed to complete the eDiary at the time of a suspected cluster headache. Once the eDiary confirms that the subject has a "qualifying" cluster headache, the subject will follow the steps provided to self-administer the study drug.

6.1.3.1 Day 1 through Week 48: Treatment of a Qualifying Cluster Headache

The following constitutes a cluster headache that qualifies for treatment with study drug:

- Severe unilateral orbital, supraorbital and/or temporal pain
- Either or both of the following:
 - 1) at least one of the following symptoms or signs, ipsilateral to the pain:
 - conjunctival injection and/or lacrimation
 - nasal congestion and/or rhinorrhea
 - evelid edema
 - forehead and facial sweating
 - miosis and/or ptosis
 - 2) a sense of restlessness or agitation

The following procedures are to be performed by the subject for a cluster headache from Day 1 through 48 weeks of the double-blind period:

• Using the eDiary, the subject will record the following to confirm the headache meets the qualifications for a cluster headache:

Cluster headache symptoms and pain assessment

- Once the qualifying cluster headache has been confirmed, subject self-administers the study drug patches. Subjects will apply two patches to the upper arm.
- Subject will continue to record the following in the eDiary, post self-administration of the patches at 5 min, 10 min, 15 min, 20 min, 30 min and 60 mins.

Cluster headache symptoms, pain assessment, and whether rescue therapy was needed

- For the cluster headache to be qualifying for study medication, no triptans or ergots are allowed within 24 hours prior to onset of cluster headache. If rescue therapy is required by the subject, rescue therapy other than a triptan or ergot is permitted at or after 20 minutes post study drug administration.
- Subject will contact the site to schedule a Visit 3 follow-up visit within 1-8 days of study drug treatment following administration of study drug.

6.1.4 Pregnancy Tests (every 4 weeks \pm 7 days)

- A urine pregnancy test will be collected on WOCBP every month from the day of randomization during the double-blind period to ensure the subject is not pregnant prior to administration of study medication.
 - Due to the COVID-19 pandemic, a urine pregnancy test kit will be sent to WOCBP for in-home testing on a monthly basis. The Investigator (or designee) will contact the subject to review and document the result.

6.1.5 Investigator (or designee) Phone Contact to Subjects (every 4 weeks \pm 3 days)

Following randomization, the investigator (or designee) will contact the subject monthly to assess for:

• Adverse events, concomitant medications and to provide study related reminders regarding eDiary use and/or C213 application instructions in advance of administering study medication for the qualifying cluster attack.

6.1.6 Investigator (or designee) Phone Contact to Subject– Following application of C213 (+ 2 days)

The investigator (or designee) will contact the subject within 2 days after C213 application to assess for:

• Adverse events and to schedule the subject for a final visit 1-8 days after C213 application.

6.1.7 Visit 3 - Day 1-8 Following Treatment of Cluster Headache / End of Study (or Early Discontinuation) Visit (+3 days)

The following procedures will be performed at the Day 1-8 / end of study (or early discontinuation):

- Collect the applicator and any unused patches and perform drug accountability
- Perform physical exam, including weight
- Record vital signs: temperature, respiratory rate (RR), blood pressure (BP), and heart rate (HR)
- Collect blood (4-hr fasting) for clinical laboratory measurements including clinical chemistries, coagulation, hematology, and serum pregnancy for WOCBP
- Collect serum pregnancy for all WOCBP
- Perform 12-lead electrocardiogram (ECG)
- Collect and review subject's eDiary data with the subject for the following:

 Subject compliance with study drug treatment and/or rescue therapy use
- Investigator Skin Assessment
- Record concomitant medications
- Review of adverse events

Due to the COVID-19 pandemic, if any subjects cannot or elect not to be seen in clinic, the Visit 3/End of Study Visit may take place via a virtual video (such as FaceTime, WhatsApp, Skype, Zoom). Any procedure such as vital signs, blood collection, and ECG, which cannot be collected on site or remote will be indicated as 'not done' in both the source documents and if prompted to specify a reason in the eCRF as due to the pandemic.

During this call, the following procedures will be performed:

- Perform drug accountability and confirm with subject that both patches were applied and arrange to have the applicator and eDiary sent back to the clinical site
- Review subject's eDiary data with the subject for the following:
 - Subject compliance with study drug treatment and rescue therapy use
- Investigator Skin Assessment
- Record concomitant medications
- Review of adverse events

• Investigator to verify results of in-home urine pregnancy test (WOCBP only)

6.2 Study Procedures

6.2.1 Informed Consent

Each study participant (or legally authorized representative) will be required to read, sign, and date the current institutional review board/independent ethics committee (IRB/IEC) approved version of the ICF. The consent process should also be documented in the study site's source documents. Informed consent must be obtained prior to performing any study-specific procedures. Both the participant and the study staff member who participated in the consent discussion with the participant must sign and date the ICF. Each study participant will be given a copy of the ICF. All participants will have an opportunity to ask questions before signing the ICF, and the study staff member who obtains consent will probe the subject to ascertain understanding of the elements of consent.

6.2.2 Inclusion/Exclusion Criteria

All inclusion criteria and none of the exclusion criteria must be satisfied prior to randomization and assignment of a CTM kit number to the subject and the start of study drug dosing.

6.2.3 Medical History, Substance Use, Cluster Headache History and Demographics

Demographic information and a medical history, including history of menopausal status, will be obtained during screening. The medical history should include all current conditions, including recent illnesses and relevant past medical history. Subjects will be asked about current use of illicit drugs, nicotine containing products, and alcohol. Information will also be obtained on the subject's history of cluster headache therapy.

6.2.4 Randomization

Randomization will be conducted at Day 1 after verifying that the participant meets all inclusion criteria and has none of the exclusion criteria. Participants who meet the study eligibility criteria and give informed consent will be randomized to one of three doses (1.9 mg, 3.8 mg, or placebo).

6.2.5 Physical Examination

A PE will be performed during screening for inclusion, at Day 1 and End of Study (or early discontinuation). The physical exam will include, but is not limited to, HEENT, dermatologic (investigator skin assessment), brief neurological, general appearance, lymph nodes, cardiovascular, respiratory, gastrointestinal and musculoskeletal examination.

6.2.6 Height and Weight

Subjects will have both height and weight measured at screening, and weight only will be collected at Day 1, and the End of Study visit (or early discontinuation). The subject must not wear shoes during the height measurement.

The subject should wear light clothing and no shoes during weight measurements. Subjects should be weighed on the same clinic scale during this study.

6.2.7 Vital Signs

All subjects will have vital signs (temperature, RR, BP, and HR) measured at screening and all subsequent visits.

Whenever possible, vital sign measurements will be taken before any blood samples are taken.

6.2.8 Clinical Laboratory Tests

Blood samples will be collected for clinical laboratory tests at screening and at the End of Study visit (or early discontinuation). Subjects must be fasting (i.e., nothing by mouth for at least 4 hours before the visit; drinking water during the 4-hour fast before clinical laboratory assessments is permitted). All samples will be processed by a central laboratory. The following parameters will be assessed:

Table 5: Clinical Laboratory Tests

Serum Chemistry	Hematology	Additional Tests
 Aspartate aminotransferase (AST) Alanine aminotransferase (ALT) Cholesterol (HDL and LDL) Bilirubin Creatinine Glomerular filtration rate (GFR) Triglyceride Alkaline phosphatase 	 Hematocrit Hemoglobin Red Blood Cell Count White Blood Cell Count Platelet Count 	 Serum and Urine Pregnancy (WOCBP only)* Urine drug screen Coagulation** PT/INR PTT

^{*} WOCBP is defined as women who are neither 1 year post-menopausal or surgically sterile.

Laboratory tests will be performed at screening and at the End of Study visit (or early discontinuation). Clinically significant abnormal values at screening may be repeated to confirm eligibility. Pregnancy tests will be performed on all women of child-bearing potential every month [+ or -7 days] after randomization to ensure no pregnancy prior to study drug administration.

The urine drug abuse screen will be performed at screening and will test for amphetamines, barbiturates, cocaine, phencyclidine (PCP), and meth/amphetamines.

The central laboratory will provide a laboratory manual and appropriate supplies (containers and labels). Laboratory values that are out of range will be identified and may be repeated at the investigator's discretion with sponsor approval. The investigator will determine if any out-of-

^{**}Coagulation sample is to be sent to Eurofins on the day of collection on dry ice.

range laboratory values that emerge during treatment are clinically significant and if so, record these on the appropriate source document and on the AE eCRF page if applicable. All clinically significant out-of-range laboratory values will be followed until they return to normal or become medically stable.

6.2.9 Twelve-Lead Electrocardiogram

The ECG, done at screening and at the End of Study visit (or early discontinuation), and will be sent to a central ECG laboratory for interpretation. ECG equipment and an ECG manual will be provided by the central ECG lab.

Any clinically significant abnormality noted on the screening ECG will be recorded on the appropriate source document and will result in exclusion of the subject from this study. The investigator may refer the subject for further evaluation and will continue to follow the subject's condition until the changes have resolved or the subject is medically stable.

6.2.10 Previous, Concomitant and Prohibited Medications

Concomitant medications will be recorded on the appropriate source document and on the appropriate eCRF at all visits including screening, randomization day, and end of study (or early discontinuation). All previous and concomitant medications taken within 90 days prior to the screening visit must be recorded in the source document and eCRF. When new medications are started and come to the attention of the investigator between scheduled visits, they will be recorded that day on the appropriate source document and on the appropriate eCRF.

No triptans or ergots are allowed within 24 hours prior to onset of current cluster headache symptoms. If rescue therapy is required by the subject, rescue therapy other than a triptan or ergot is permitted at or after 20 minutes post study drug administration. Ergots and triptans may be resumed 24 hours after dosing with study medication.

No lotions, ointments or powders applied to the skin immediately before (within an hour) or for 24 hours after applying the patches are allowed.

Table 6 lists all prohibited medications. Medications listed in Table 6 are prohibited from 7 days prior to screening through the final visit.

Table 6: Prohibited Concomitant Medications

Drug Type	Medication
Prescription anticoagulants	Entire class
Monoamine oxidase inhibitors	Entire class
Potent CYP450 3A4 Inhibitors	Ketoconazole
	Erythromycin
	Clarithromycin
	Cimetidine
	Grapefruit
CYP450 1A2 Inhibitors/Inducers	Ciprofloxacin

Drug Type	Medication
	Enoxacin
	Fluvoxamine
	Alpha-Naphthoflavone
	Furafylline
	Omeprazole (OTC)
	Lansoprazole (OTC)
	Fluvoxamine
	Enoxacin
	Phenytoin
	Rifampin
	Ritonavir
	teriflunomide
	Methoxsalen
	Mexiletine
	Tobacco Cigarettes

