- diagnostic criteria). Diagnostic criteria must include a history of at least 5 attacks not attributed to any other disorder that include all of the following criteria:
- a) Severe or very severe unilateral orbital, supraorbital and/or temporal pain lasting 45-180 minutes (average, when untreated)
- b) Either or both of the following:
 - (1) At least one of the following symptoms or signs, ipsilateral to the pain:
 - (a) Conjunctival injection and/or lacrimation
 - (b) Nasal congestion and/or rhinorrhea
 - (c) Eyelid edema
 - (d) Forehead and facial sweating
 - (e) Miosis and or/ptosis
 - (2) A sense of restlessness or agitation
- c) Attacks have a frequency between one every other day and eight per day for more than half of the time when the disorder is active.
- d) Not better accounted for by another ICHD diagnosis
- 4. Cluster history during the 12-month period prior to the screening visit must include:
 - a) At least 1 cluster period
 - b) Averaging 2-6 headaches per day
 - c) Lasting at least 7 days
- 5. Subject can distinguish cluster headaches from other headaches (i.e., migraine and tension-type headaches)
- 6. Women of child-bearing potential must not be pregnant, must agree to avoid pregnancy during the trial, and must use one of the following or be surgically sterilized: intrauterine device, or a hormonal contraceptive
- 7. Able to understand the operation of the electronic diary and able to apply the demo study drug patch correctly.

Exclusion Criteria:

Subjects presenting with any of the following will not be included in the study:

- 1. Contraindications to triptans
- 2. Use of any prohibited concomitant medications within 7 days of screening
- 3. History of hemiplegic migraine or migraine with brainstem

aura

- 4. Participation in another investigational trial within 30 days or 5 half-lives of investigational product (whichever is longer).
- 5. Previous M207/C213 exposure in a clinical trial
- 6. Subject has other significant pain problems that might confound the study assessments in the opinion of the investigator
- 7. Diagnosis of any malignant disease (other than adequately treated or excised non-metastatic basal cell carcinoma or squamous cell carcinoma of the skin) within the 5 years prior to screening
- 8. History of unstable psychiatric illness requiring medication or hospitalization in the 12 months prior to study screening
- 9. Subjects who have a known allergy or sensitivity to zolmitriptan or its derivatives or formulations

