6 STUDY PROCEDURES AND SCHEDULE

6.1 Study Schedule

A schedule of study procedures is presented in Table 4.

Table 4: Schedule of Study Procedures

	VISIT 1 ¹ Screening [+3 days]	VISIT 2 Randomization Day ¹	48 Week Double-blind Period [+ or – 7 days]	VISIT 3 End of Study (or Early Discontinuation) [+ 3 days]
Procedure	Up to 1 week prior to Randomization	Day 1 – start of double-blind period	Day 1 – Day 336	Day 1-8
Informed Consent	X			
Inclusion/Exclusion Criteria	X	X		
Medical History including Cluster headache, nicotine, alcohol use, and substance abuse history	X			
Demographics	X			
Randomization		X		
Physical Exam	X	X		X
Weight ² /Height	X	X^2		X ²
Vital Signs	X	X		X
Adverse Events Collection		X		X
Concomitant meds/therapies Collection	X	X		X
Chemistry, coagulation & Hematology (fasting) ³	X ³			X
Serum or Urine Pregnancy 4 (only for WOCBP)	X - Serum	X – Urine dipstick	X – Urine dipstick ⁴	X - Serum
Drug Abuse Testing	X			
12-lead ECG	X			X
Train on patch application using demonstration patches		Х		
Train/dispense eDiary		X		
Dispense CTM		X		
Study Drug Self- Administration			X	
Subject eDiary Assessments			X	
Investigator Skin Assessment		X		X
Investigator Phone call to subject ^{5, 6}			X ^{5, 6}	
Collect Unused Patch(es) and Applicator/Perform Drug Accountability				X
Collect eDiary				X

- Qualifying headache and treatment of a cluster headache must occur within 48 weeks of randomization
- Both height and weight at screening only and weight only at visit 2 and 3
- Clinically significant abnormal lab values may be repeated and if not clinically significant on repeat, subject may be eligible for randomization
- ⁴ Urine pregnancy for WOCBP will be collected monthly [+ or 7 days] after randomization day 1 to ensure no pregnancy prior to study drug administration.
- Following randomization, the investigator (or designee) will contact the subject monthly [+ or 3 days] to assess for adverse events, concomitant medications and to provide study related reminders regarding eDiary use and/or C213 application instructions in advance of the qualifying cluster attack.
- The investigator (or designee) will contact the subject within 2 days after C213 application to assess for Adverse Events and to schedule the subject for a final visit 1-8 days after C213 application.

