8.1 Reporting Period

Collection of systemic and skin AEs will be initiated after the ICF has been signed and will conclude when the post-study procedures are completed (or Early Discontinuation). The investigator will also report to the Medical Monitor and Pharmacovigilance any SAEs that come to his/her attention that occur within 30 days after study drug administration.

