8.2 Adverse Event Definitions

8.2.1 Adverse Events (Adverse Experiences)

An AE is any untoward medical event that occurs in a clinical investigation, where a subject is administered a medicinal (investigational) product or medical device, and which does not necessarily have a causal relationship between the event and the treatment. An AE can be any unfavorable and unintended sign or symptom, including clinically significant abnormal laboratory result, concomitant illness, or worsening of an existing medical condition.

A Treatment Emergent Adverse Event (TEAE) is an event that emerges during treatment having been absent pre-treatment or worsens relative to the pre-treatment state.

Collection of systemic and skin AEs will be initiated after the ICF has been signed and conclude when the post-study procedures are completed (or Early Discontinuation). This includes the time between screening and the first dosing.

Abnormal laboratory tests that are clinically significant, as determined by the investigator, should be reported as AEs if:

- the test result is associated with accompanying symptoms;
- the test result requires additional diagnostic testing or medical/surgical intervention;
- the test result leads to discontinuation from the study, significant additional concomitant drug treatment, or other therapy;
- the test result is considered to be an AE by the investigator or sponsor.

Merely repeating an abnormal test, in the absence of any of the above conditions, does not constitute an AE. Any abnormal test result that is determined to be an error does not require reporting as an AE.

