8.3 Documentation and Reporting of Adverse Events by Investigator

Each AE is to be assessed to determine if it meets the criteria for an SAE. If an SAE occurs, expedited reporting will follow local and international regulations, as appropriate.

All AEs, both expected and unexpected, occurring during this clinical trial must be recorded on the AE page of the eCRF. AEs will be described in precise medical terms, along with the date and time of onset and the date and time of resolution, action taken and outcome. In order to avoid vague, ambiguous or colloquial expressions, the AE should be recorded in standard medical terminology rather than the subject's own words. Whenever possible, the Investigator should group together into a single term signs and symptoms which constitute a single diagnosis. Each AE is to be evaluated for duration, severity, seriousness and causal relationship to the investigational drug. The severity of the AE and its relationship to the test product will be assessed by the Investigator. When reporting SAEs, the AE form of the eCRF and the SAE form must be completed in a consistent manner. For example, the same AE term should be used on both forms.

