## 3.4 Minimization of Missing Data / Dropout rate

It is important to avoid missing data from clinical trials. The following strategies are designed to minimize drop-outs and missing data in this study:

- Minimizing the burden on subjects, with only three visits scheduled over the course of the trial (with reasonable visit window flexibility).
- Providing payment for subjects' time at clinic visits, as approved by the Institutional Review Board.
- Allowing rescue medication/therapy at or after 20 minutes post patch administration.
- Training of site personnel on emphasizing to subjects the importance of completing the eDiary assessments in order to minimize missing data.
- Employing an eDiary training module for subjects to complete prior to the distribution of the eDiary.
- Using alarms and reminder alerts for eDiary data entry.
- Instituting an eDiary reminder card for subject use that shows the timepoints when subjects need to enter data.
- Having a web portal available to site personnel where missing eDiary data can
  be easily identified so site personnel can be retrained on the importance of
  emphasizing to subjects the need to complete eDiary assessments, if
  necessary.

Due to the COVID-19 pandemic, the protocol was amended in April 2020 to allow for a visit 3 telemedicine visit. If any subjects cannot or elect not to be seen in clinic, the Visit

Protocol: CP-2019-001 Page 11 of 26

Final Version 1.0

3/End of Study Visit may take place via a virtual video (such as FaceTime, WhatsApp, Skype, Zoom). During this call, the Principal Investigator will assess for adverse events, skin reactions where C213 was applied, concomitant medication/rescue medication use, and drug accountability. For the subjects who are female of child-bearing potential, the sites will send a urine pregnancy test kit (monthly per protocol) and after dosing, verify that there is no pregnancy. In addition, the Sponsor, on a case by case basis, will consider allowing an 'out of window' Visit 3/End of Study Visit (in person). Any procedure such as vital signs, blood collection, and ECG which cannot be collected on site or remote will be indicated as 'not done' in both the source documents and eCRF, and if prompted, with a reason specified in the eCRF as due to the pandemic.

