#### 10.1 Adverse Events

All AEs, treatment-emergent adverse events (TEAEs), and SAEs will be coded using MedDRA, version 22.0.

Adverse events are categorized as either pre-treatment adverse events or treatmentemergent adverse events based on the response to the CRF question "Did the AE occur prior to patch administration?"

An AE summary table or listing will be presented for the following:

- TEAEs by severity
- TEAEs leading to study drug discontinuation
- TEAEs by relationship
- SAEs

Summaries of incidence rates (frequencies and percentages) of individual TEAEs by MedDRA SOC and preferred term will be prepared if there are a sufficient number of adverse events.

Each subject will be counted only once within each summation level (SOC; preferred term).

In the AE data listings, all AEs will be displayed. AEs that are treatment-emergent will be flagged.

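### Treatment-emergent events are counted up to Visit 3 while other triptans and ergots are allowed from 24 hours, so systemic event rates can include non-study triptan reactions that no planned output separates

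*Protocol*

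**What the plan says.** **Which events count.** SAP 7.3.1 and 10.1 sort adverse events by one CRF question: "Did the AE occur prior to patch administration". Events before the patch are pre-treatment and all others are treatment-emergent. No end time is set. Protocol 8.2.1 words it differently, as "an event that emerges during treatment having been absent pre-treatment or worsens relative to the pre-treatment state", also without a limit in hours or days.

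**How long events are collected.** Protocol 8.1 ends collection when the post-study procedures are done. Under Protocol 6.1 (Table 4, footnotes) the site is to "schedule the subject for a final visit 1-8 days after C213 application". Table 4 and section 6.1.7 add a +3 day window, and SAP 3.4 lets the sponsor accept an out-of-window in-person visit case by case.

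**What else may be taken.** Protocol 6.2.10: "Ergots and triptans may be resumed 24 hours after dosing with study medication". The rule is the same in every arm. The study treatment is one 30-minute application (SAP 11.2).

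**What is recorded.** Protocol 8.3 has events described "along with the date and time of onset and the date and time of resolution". SAP 11.1 defines a medication as concomitant only if it starts no later than 5 days after the patch, although all medications are listed.

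**What is reported.** SAP 10.1 plans treatment-emergent events by severity, by relationship and by discontinuation, plus serious events, each as a table or listing. Incidence by SOC and preferred term follows only if there are enough events. None of these splits events by time from dosing or by use of another triptan.

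**The concern.** Comparing safety with placebo and assessing dose-response for tolerability are secondary objectives (Protocol 2.2, SAP 2.1.2). C213 is a triptan given once. From 24 hours a subject may take another drug of the same class, and a reaction to that drug is then counted under the randomised arm. Resumption before Visit 3 is plausible, because inclusion criterion 4 asks for a cluster period in the previous 12 months "Averaging 2-6 headaches per day".

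If such events occur, they raise the systemic event rate in all three arms and make the contrast with placebo harder to read. The systemic signal is likely to be small, so a few such events could matter. In the earlier migraine study (Protocol Table 2), musculoskeletal events occurred in 0/83, 1/80, 2/87 and 4/83 subjects from placebo to 3.8 mg.

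**Working it through.** **1. The documents' own figures.** There is no planned safety rate or safety power to reproduce. The only power figure concerns efficacy and does not bear on this point. The Table 2 percentages reproduce for placebo versus 3.8 mg:
- musculoskeletal: 0/83 = 0.0% and 4/83 = 4.8%
- general and application-site: 12/83 = 14.5% and 38/83 = 45.8%

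**2. Share of the window in which other triptans are allowed.** If Visit 3 is D days after the patch, the share is (D - 1)/D.

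| Visit 3, days after patch | Share after 24 h |
|---|---|
| 1 | 0% |
| 2 | 50% |
| 8 | 7/8 = 87.5% |
| 11 (8 + 3) | 10/11 = 90.9% |

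This is a share of time, not of risk.

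**3. Effect on the comparison.** Let p be the systemic event rate without other triptans. Let b be the chance of an event from a resumed triptan, equal across arms and independent of p. The observed rate is

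p' = 1 - (1 - p)(1 - b) = p + (1 - p)b.

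The observed risk difference is then (p_C213 - p_placebo)(1 - b). It shrinks only by the factor 1 - b, while the ratio shrinks faster because b is added to a small placebo rate.

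The documents give no value for b. Assume that 25% to 80% of subjects resume and that 5% to 20% of those have an event from the resumed drug. Then b runs from 0.25 x 0.05 = 1.25% to 0.80 x 0.20 = 16%. A value of 15% lies within this range.

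| Starting rates (placebo, C213) | b | Observed placebo | Observed C213 | Difference (points) | Ratio |
|---|---|---|---|---|---|
| 5%, 20% (assumed) | 0 | 5.0% | 20.0% | 15.0 | 4.0 |
| | 1.25% | 6.2% | 21.0% | 14.8 | 3.4 |
| | 5% | 9.75% | 24.0% | 14.25 | 2.5 |
| | 15% | 19.25% | 32.0% | 12.75 | 1.7 |
| | 16% | 20.2% | 32.8% | 12.6 | 1.6 |
| 0%, 4.8% (Table 2, musculoskeletal, 3.8 mg) | 0 | 0.0% | 4.8% | 4.8 | not defined |
| | 1.25% | 1.25% | 6.0% | 4.8 | 4.8 |
| | 5% | 5.0% | 9.6% | 4.6 | 1.9 |
| | 16% | 16.0% | 20.0% | 4.0 | 1.25 |

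Across the whole range the difference keeps 84% to 99% of its size. The ratio in the first example falls from 4.0 to between 3.4 and 1.6.

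**4. Can the periods be separated?** Largely yes, because onset date and time are collected. The medication side is weaker. SAP 7.3.1 and 11.1 work with dates only, and a triptan whose recorded start is on days 6 to 11 is listed but not summarised as concomitant, although events on those days are treatment-emergent.

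**The case against.** The case against a serious bias is strong, and much of it stands.

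- **Unequal use.** A reader might infer that placebo subjects take more triptans afterwards, which would make C213 look better tolerated than it is. With assumed later-event chances of 10% on C213 and 20% on placebo, the rates become 1 - 0.80 x 0.90 = 28% and 1 - 0.95 x 0.80 = 24%, and 15 points shrink to 4. The documents do not support that split. Each subject treats one attack, attacks average 45-180 minutes untreated under the inclusion criteria, and triptans and ergots stay barred for 24 hours in every arm. By then the treated attack should be over in all arms.
- **Number of later attacks.** A reader might also multiply 2-6 attacks a day by the 7 days after the first 24 hours and expect 14-42 more. The 2-6 figure is an entry criterion on past history, not a forecast after dosing.
- **Choice of measure.** The SAP plans frequencies and percentages, with no safety risk ratio and no between-arm safety test. On the difference scale the effect under equal use is modest.
- **Main signal.** Application-site reactions dominate Table 2, and a non-patch triptan would not be expected to cause them. The assumed 20% systemic rate is well above anything systemic in that table, though the table shows only events in two or more subjects.
- **Existing safeguards.** Causality definitions take account of concomitant drugs (Protocol 8.2.1.4), a call within 2 days asks about events (6.1.6), and all events and medications are listed.
- **A 24-hour window is not clean either.** Non-triptan rescue is allowed from 20 minutes and could differ by arm. Making 24 hours the main comparison would also demote later systemic events.

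The safeguards do not close the gap. The relationship rating asks a blinded investigator to tell one triptan from another. Unknown causality is handled as related for reporting (Protocol 8.2.1.4), and a missing rating is imputed as related (SAP 7.3.1). Onset times are recorded, but no planned output uses them to split the period.

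**Conclusion.** The point holds in a limited form. Every event after the patch and up to Visit 3 is treatment-emergent, other triptans and ergots are allowed from 24 hours, and the planned outputs do not separate the two periods. Systemic rates can therefore include events from non-study triptans, which would raise the background in every arm.

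Under equal use the ratio between arms suffers most, and the difference keeps 84% to 99% of its size for b between 1.25% and 16%. These figures rest on assumed resumption and event rates and on independence. The documents supply neither rate, so they show that dilution is possible, not that it occurs. They give no basis for expecting more resumption on placebo, and so none for saying that the comparison is biased in favour of C213. Events before the patch are not affected, and application-site events largely are not.

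This is a cheap improvement to how systemic tolerability is displayed. It does not invalidate the safety analysis. Because enrolment fell well short of plan (SAP 12), any comparison will be imprecise whichever window is used.

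**What to change.** - **SAP 10.1, display.** Keep the through-Visit-3 summary as planned. Add a by-arm display of systemic treatment-emergent events split by onset within 24 hours of the first patch versus later, from the recorded onset date and time. Count an event dated on the dosing day or the next day with no time as within 24 hours.
- **SAP 10.1, listing.** Flag events with onset on or after the date of the first post-dose triptan or ergot. Where both fall on the same day and no time is available, mark the order as undetermined.
- **SAP 11.1.** Extend the 5-day limit on concomitant-medication start dates to the end of adverse event collection, so that the medication and event windows match.

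The cost is one extra display and one listing flag. Counts will be sparse, and some same-day cases will stay undetermined. The split uses data the protocol already collects, and no clinical rule changes.
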